We will include Type 2 DM patients of both sexes and from all ethnic groups between the ages of 25 and 80 years, with 25(OH)D₃ levels <25 ng/ml. We will include those diabetes patients with HbA1c between 5.5%-9.5% who are not on insulin therapy and without recent weight loss of more than 5% within 3 months prior to screening. Each patient must have a 24h Ambulatory Blood Pressure (ABPM) with mean systolic BP \geq 120 mmHg and / or mean diastolic BP \geq 80 mmHg without BP lowering medications or after stopping any BP medication for 2 weeks or more (46). We will exclude pregnant women, patients with ABPM showing mean systolic BP (SBP) >160 mmHg or mean diastolic BP (DBP) >100 mmHg, those with heavy alcohol consumption (males >2 drinks per day and females >1 drink per day), patients following extreme diets (Atkins, South Beach diet), those with stage 4 chronic renal failure (calculated by modification of diet in renal disease eGFR equation) and/or patients with >2 + proteinuria on urine dipstick.

Subject Screening

We will screen diabetic hypertensive or pre-hypertensive patients without BP lowering

medications or those who control BP with any anti-hypertensive medication with no known history or clinical manifestations of cardiovascular disease or proteinuria per clinical judgement. If the patient and their physician are agreeable, we will assess the patient's cardiovascular risk and clinical manifestations, and then stop their medication and check their blood pressure supply an automatic blood pressure monitor for them to report blood pressure measurements to the research coordinator 3x/week for 2 weeks (time based on the pharmacokinetics of the most commonly prescribed BP medications). At the end of this wash-out period, we will complete the screening by measuring 24h blood pressure using an ambulatory device to assure that the patient's blood pressure is within our inclusion criteria and will not place the patient at higher risk. If the patient's blood pressure remains below ABPM mean SBP 160 and mean DBP100 mmHg, then we will enroll them in the study with continued close monitoring of their blood pressure.

Protocol

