The recruitment process at the VA medical center will consist of obtaining a print out of potentially eligible patients identified during a database search of VISTA for patients meeting inclusion criteria. Screening would occur by a computer search of VISTA data to identify individuals with diabetes (ICD-9 250.x or use of diabetic medications) and 25 OH vitamin D levels less than 20ng/dl. Once this list is generated, then a letter will be sent to these individuals with the details of the study and a contact phone number. If the patient does not call for 2 weeks after the receipt of the letter, then we will call them to give them more study specifics, address any questions or concerns, and assess study suitability. Also patients scheduled to be seen in high potential clinics will be screened using the above criteria. Providers will be given information regarding the study and their permission will be obtained to approach and screen their clinics. The listings will contain the patient's name, SSN and clinic visit information. Individuals will be pre-screened utilizing CPRS for inclusion/exclusion criteria per protocol. If a patient is potentially eligible, a note will be entered in CPRS and sent to their PCP to notify them that their patient is being contacted for possible recruitment into a clinical trial. Also, the study physicians may identify potential patients during their routine clinical duties. If a patient's file is being reviewed or a patient is seen in the clinical area that is possibly eligible, the physician may notify the coordinator for screening. Identified patients will be sent to Washington University for their screening visit if interested. The screening visit or any study procedures will not be conducted until the consent form is signed at Washington University.

At the initial screening visit, anthropometric measurements, ECG, BP and blood samples for CBC, comprehensive metabolic panel (CMP), HbA1c, pregnancy test, urinalysis, urinary albumin-creatinine ratio and 25(OH) D₃ level will be obtained at the Clinical Trial Unit (CTU) or Storz Research Building (Table 1). If the patient is deemed to have low cardiovascular risk and the attending or primary physician agrees, the patient will be advised to stop one anti-

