Appropriate data transformations or non parametric methods will be used as appropriate. We proposed to recruit 120 patients for this study. Assuming a 20% dropout rate, 90% power calculation was performed to determine the magnitude of between-group differences that can be detected with the sample size of 48 patients per group. The type-I error rate was set at $\alpha=0.05$ with a two-tailed unpaired t-test and conservative projected standard deviations (SDs) based on the investigator's pilot data and Pfeifer, et al.⁵⁷ The planned study with 48 patients completing the intervention affords excellent power to detect meaningful differences for the primary outcomes; with minimum detectable differences ranging between 10 to 15 mm Hg and 5 to 10 mm Hg for SBP and DBP, respectively. Although the study is not powered for the secondary endpoint of FMD, the study yields power of more than 0.90 to detect a minimum difference of 2% (assuming an SD=2.5).

Data and Safety Monitoring Plan

We will minimize the patient's risks by careful screening and frequent physician visits (every 2 weeks for the first 6 weeks) to the clinic, where the patient will be educated about the signs and symptoms of hypertension, hyper- and hypocalcemia and kidney stones. We will also monitor the patients' BP, serum calcium, and urinary calcium levels during these visits. To prevent vitamin D toxicity, we will assess a random sample of vitamin D pill content.

All data will be used for research purposes. The risk of loss of confidentiality will be minimized by adherence to HIPAA guidelines established by Washington University. Data analysis will be based on the intention-to-treat principle where all patients will be analyzed as part of their randomization group regardless of subsequent events. We will also perform a secondary analysis on patients that complete at least 8 weeks of treatment. ClinPortal will be used to collect, store and disseminate project-specific clinical and translational research data

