Our *Data Safety Monitoring Plan* includes thorough documentation of any and all Serious Adverse Events (SAE) and reporting to the Human Research Protection Office (HRPO), the Research Subject Advocate and GCRC Advisory Committee. The participant's side effect log will be reviewed at the time of any event, and all participants that note significant concerns about side effects that cannot be easily and safely addressed will be told to stop the study drug. Reporting of adverse events will be conducted with oversight by the Principal Investigator (PI) and the Research Subject Advocate. Summary reports will be provided to the HRPO and the Research Subject Advocate every six months. In case of a SAE, the research coordinator or PI will report the event to the DSMB and to the HRPO according to the current HRPO guidance document. The PI will determine if the SAE is causally related to the study. Other possibly concerning objective findings that indicate potential for harm will be reviewed with the PI, [name], and lead to stopping the study for that subject if either the PI or any nurse caring for the patient in the GCRC feels the participant could be harmed by continuing the study. Any clear evidence of potential harm will lead to stopping the study for that patient. The HRPO will get a summary of the situation unless the dropout is secondary to participant's personal reasons and unrelated to the study. An interim efficacy analysis will be performed when 60 of the targeted 120 subjects have been enrolled. This analysis will focus on the primary endpoint and will permit us to make one of the following decisions: a) Stop the study early if the data suggest that efficacy has already been achieved. b) Stop the study early for reasons of futility if the data suggest that it is unlikely that efficacy will ever be achieved. c) Continue the study with an increase in the target sample size if the data indicate smaller effect sizes that were initially projected but that an achievable increase in the sample size will yield adequate statistical power. d) Continue the study as planned if effect sizes appear to be approximately as projected. The interim analysis will be conducted in accordance with guidelines set forth by the O'Brien Fleming stopping rule.¹ We emphasize, however, that this will only be a guideline. Any final decision to modify the sample size or to stop the study early will be based on multiple considerations that also include efficacy with respect to important secondary outcomes and the consistency of results across key subgroups. Our study will be conducted with the ideas of justice, beneficence and autonomy having primary importance.

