
The DSMB will be informed of all Serious Adverse Events (SAEs). An SAE will be defined as an event which results in any of the following outcomes: death, life-threatening event, persistent or significant disability, inpatient hospitalization or prolongation of an existing hospitalization, or congenital anomaly. In addition, any symptomatic patients with stroke, intracranial bleeding, heart attack, heart failure, symptomatic hypocalcemia/ hypercalcemia, or increased urinary calcium/creatinine ratio >1.0 that is unresponsive to fluid therapy (at least six to eight glasses of water per day for 5 days) will be considered to be an SAE and withdraw. The PI will determine if the SAE is causally related to the study without regard to knowledge of treatment group assignment. Any patient with an SAE which is determined by the PI to be possibly or probably related to the study intervention will be withdrawn from the study. All SAEs will be reviewed by the DSMB to confirm the PI's assessment of causality and will be reported to the Institutional Review Board (IRB) and CARS Research Subject Advocate. Symptomatic subjects who develop sustained severe symptomatic hypertension during the study defined as SBP >160 mmHg and/or DBP >100 mmHg by office BP measurements (confirmed by ABPM) will be evaluated by [name] and/or [name] and he/she will determine if patient will be withdrawn by determine the clinical risk to develop hypertensive complications. The physician will also determine if there is a clear triggering factor that is causing the increase in blood pressure and if it is easy to resolve it before patient is dropped from the study. The participant's primary care doctor will be notified and antihypertensive therapy will be started as per their recommendation. If patients do not have a primary care doctor, antihypertensive therapy will be started and they will be referred to a medical provider for further management

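### The only on-study blood pressure action level is worded for symptomatic patients, although the same 160/100 limits bar entry with or without symptoms

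*Combined protocol and SAP*

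**What the plan says.** **Entry.** The Inclusion/Exclusion criteria state: "We will exclude pregnant women, patients with ABPM showing mean systolic BP (SBP) >160 mmHg or mean diastolic BP (DBP) >100 mmHg". The Protocol section adds that mean BP on ABPM must lie within 120-160/80-100 mmHg. Neither text mentions symptoms. Patients qualify untreated or "after stopping any BP medication for 2 weeks or more". The Protocol section describes wash-out as stopping one agent, so the document is not uniform on whether every patient is fully off treatment at entry.

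**During the study.** The Data and Safety Monitoring Plan has one rule with a BP level. It concerns "Symptomatic subjects who develop sustained severe symptomatic hypertension during the study defined as SBP >160 mmHg and/or DBP >100 mmHg", measured in the office and confirmed by ABPM. A named physician evaluates the patient, looks for a correctable cause and decides on withdrawal. The primary care doctor is told, and drug treatment starts on that doctor's advice. A patient with no such doctor is started on treatment and referred. The first target is 160/110 mmHg within several days.

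**Other cover.** For a patient still within limits after wash-out, Subject Screening says: "then we will enroll them in the study with continued close monitoring of their blood pressure". Safety visits with seated BP run every two weeks for six weeks and monthly after that. Table 1 lists a physician assessment at weeks 4, 8, 12 and final. The Data and Safety Monitoring Plan also states: "Other possibly concerning objective findings that indicate potential for harm will be reviewed with the PI". Such findings are to "lead to stopping the study for that subject if either the PI or any nurse caring for the patient in the GCRC feels" that continuing could harm the patient. A further sentence makes stopping mandatory once potential harm is clear.

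**The concern.** The entry limit is a judgement about BP level: the qualifying ABPM is there to show that taking part will not raise the patient's risk. Nothing in that reasoning depends on symptoms, and it does not lapse at randomization. Yet the on-study rule uses the same two numbers and states the symptom condition twice.

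The patients have type 2 diabetes, and some have had antihypertensive treatment stopped in order to qualify. If BP later stays above the protocol's own entry limit and they feel well, no stated level obliges anyone to evaluate them under this rule, tell their primary care doctor or decide about treatment. Those steps then rest on how staff apply general clauses.

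**Working it through.** The plan gives no figure to reproduce. The check is a comparison of texts with two short pieces of arithmetic.

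**1. Limits compared.**

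| | Entry | On study |
|---|---|---|
| Systolic | >160 mmHg | >160 mmHg |
| Diastolic | >100 mmHg | >100 mmHg |
| Measurement | ABPM mean | Office, confirmed by ABPM |
| Symptoms needed | No | Yes, stated twice |

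The numbers match. Besides the route of measurement, the symptom condition is the main difference.

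**2. Rules counted.** I looked at every place where BP is monitored or acted on after enrolment: Subject Screening, Protocol, Data and Safety Monitoring Plan and Table 1. Rules that name a BP action level: 1. Of these, rules that reach asymptomatic patients as worded: 0. The list of serious adverse events does not include asymptomatic hypertension.

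**3. What the other text supplies.**

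| Text | BP seen | Physician involved | BP level | Primary care notice | Treatment step |
|---|---|---|---|---|---|
| Close monitoring after enrolment | Yes | Not stated | No | No | No |
| Safety visits and Table 1 | Every visit | Weeks 4, 8, 12, final | No | No | No |
| Review of concerning findings | If noticed | Principal investigator | No | No | No |
| Stop when potential harm is clear | If judged so | Not stated | No | No | No |

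In Table 1, seated BP is taken at 5 post-baseline visits (weeks 2, 4, 8, 12 and final), and 4 of the 5 include a physician assessment. The safety plan text also promises physician visits every two weeks up to week 6. Contact is therefore well covered; the last three columns are empty throughout.

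**4. The same contrast within the safety plan.** Serum calcium >10.5 mg/dl or a urinary calcium/creatinine ratio >1.0 applies both at screening and on study, by number, with no symptom condition. BP is handled differently.

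**5. Goal against trigger.** Systolic: 160 − 160 = 0. Diastolic: 110 − 100 = 10 mmHg. Anyone with systolic at or below 160 and diastolic above 100 and up to 110 meets the diastolic trigger and is already at goal; 155/105 is an example. Widening the rule without changing the goal would carry this mismatch to more patients.

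**6. ABPM available for confirmation.** Table 1 has ABPM at week 8 and final, so 5 − 2 = 3 of the 5 visits would need an unscheduled one. Counting the week-6 visit implied by the Protocol section, it is 6 − 2 = 4 of 6. These counts measure the cost of the fix, not harm.

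**The case against.** The best opposing case has four parts.

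- **Loose drafting.** The clause that defines the hypertension lists only numbers, so the symptom words may be unintended. This is plausible and cannot be settled from the text. If it is right, rewording restores the intended meaning; if not, rewording closes a real gap. The edit is the same.
- **Physicians already see these patients.** Over 16 weeks of treatment most visits pair a BP reading with a physician assessment, and two of the general clauses are worded as mandatory. This stands, and it limits the point considerably. What is missing is a stated level and the steps that follow from it.
- **The existing rule also relies on judgement.** Withdrawal is the physician's decision, and treatment usually follows the primary care doctor's advice. This stands too. The gain from a change is a required evaluation and a required notice, not compulsory treatment.
- **Entry is guarded, and the same number need not serve twice.** Wash-out proceeds only "If the patient is deemed to have low cardiovascular risk and the attending or primary physician agrees", with home readings three times a week for two weeks and a qualifying ABPM. That lowers risk at entry but gives no on-study rule. An on-study limit could reasonably differ from the entry limit; here the plan chose the same numbers.

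A reader might infer that asymptomatic patients go unmonitored, or that the plan deliberately leaves them without action. The documents support neither: monitoring and physician contact are scheduled, general stopping clauses apply without symptoms, and nothing shows that the exclusion was intended.

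**Conclusion.** As worded, the only on-study BP action level does not reach patients without symptoms. Evaluation under that rule, primary care notice and a treatment decision are therefore not required at any stated level for a patient with sustained, ABPM-confirmed BP above 160 and/or 100 who feels well. Existing visits and general clauses reduce the consequence but do not supply those steps.

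The size is unknown. The documents give no rate of on-study BP above these limits. The recruitment target of 120 is the pool at risk, not the number affected; those affected are only patients who entered within 160/100 and later had confirmed, sustained, symptom-free BP above it. The 10 mmHg diastolic mismatch between goal and trigger is certain, but it is a secondary drafting point. Although 160/110 is described as an initial goal, it would leave some patients above the trigger.

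The conclusion rests on reading the symptom words as they stand. It calls for a change worth making, not for a halt to the trial.

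**What to change.** Reword the hypertension rule in the Data and Safety Monitoring Plan as one rule for all patients:

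- Sustained systolic BP >160 and/or diastolic BP >100 mmHg by office measurement, confirmed by ABPM (unscheduled if none is due), triggers evaluation by the named physician and notice to the primary care doctor, regardless of symptoms.
- Withdrawal stays with the evaluating physician. Starting an antihypertensive is left to the primary care doctor or, if there is none, to the evaluating physician with referral.
- Set the initial BP goal at or below 160/100 so that it no longer exceeds the trigger.
- Record every antihypertensive started on study, with drug and start date, so that use can be reported by arm.

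The cost is a few reworded sentences, two data fields, and a few extra evaluations and unscheduled ABPMs. The main statistical drawback is that some on-drug BP values would enter the primary outcome under the intention-to-treat analysis. The present rule already permits this for symptomatic patients, and the Statistics section does not mention on-study antihypertensives, so the record is useful either way.

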that is covered by their insurance. The initial goal is to reduce blood pressure to 160/ 110 mm Hg over several days, we will follow these patients closely until this ambulatory BP is achieved. Patients with increased urinary calcium/creatinine ratio >1.0 that are unresponsive to oral fluid therapy, will be evaluated in the CRU to determine whether IV fluid therapy is required. We will follow this patients until they achieve urinary calcium/creatinine ratio <1.0. Patients with asymptomatic hypocalcemia that are unresponsive to increased PO Calcium intake we will supervise calcium intake by clinic visits and follow until plasma calcium levels return to normal. If the patient becomes symptomatic and requires a hospitalization, the patient will be withdrawn from the study. Patients that have completed at least 8 weeks in the study and are withdrawn for medical reasons, will continue to be evaluated every 4 weeks for BP monitoring, plasma calcium levels and urinary calcium and creatinine ratio until completing 16weeks from the initiation of the trial. At 16 weeks AMBP monitoring and FMD and macrophages will be obtained.

Summary reports of all Adverse Events (non-serious AEs and SAEs) will be provided to the DSMB before each scheduled meeting and at least every 4 months. If the PI or the DSMB determine that there are an unacceptable number of AEs and/or SAEs reported, the PI may request that the DSMB review (or the DSMB may independently decide to review) the events by unmasked treatment group. If treatment-emergent AEs or SAEs are occurring at an unacceptable rate, the DSMB may recommend to the PI that the study be halted or that the protocol be modified.

References

3. Killilea T. Long-term consequences of type 2 diabetes mellitus: economic impact on society and managed care. *Am J Manag Care* 8:S441-9, 2002
4. Tight blood pressure control and risk of macrovascular and microvascular complications in type 2 diabetes: UKPDS 38. UK Prospective Diabetes Study Group. *Bmj* 317:703-713, 1998

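### For on-study hypertension, the diastolic figure that triggers treatment (>100 mmHg) and the one that ends close follow-up (110 mmHg) do not agree

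*Combined protocol and SAP*

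**What the plan says.** Three parts of the combined protocol and SAP bear on this.

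- **Trigger (Data and Safety Monitoring Plan).** The rule concerns "Symptomatic subjects who develop sustained severe symptomatic hypertension during the study", with the limits "SBP >160 mmHg and/or DBP >100 mmHg by office BP measurements (confirmed by ABPM"). A study physician assesses the subject and decides on withdrawal. The subject's primary care doctor is told, and "antihypertensive therapy will be started as per their recommendation". A subject without such a doctor is also started on therapy and is referred on.
- **Goal (same section, directly afterwards).** "The initial goal is to reduce blood pressure to 160/ 110 mm Hg over several days"; and "we will follow these patients closely until this ambulatory BP is achieved".
- **Entry limits.** Inclusion/Exclusion criteria rule out an ambulatory recording with "mean systolic BP (SBP) >160 mmHg or mean diastolic BP (DBP) >100 mmHg". The Protocol section repeats the ceiling, with an ambulatory qualifying range of 120-160/80-100 mmHg. For subjects on blood pressure drugs, the qualifying recording is made "after stopping any BP medication for 2 weeks or more".

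The figure of 110 appears once, in the goal. Everywhere else the upper diastolic limit is 100.

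**The concern.** A rule of this kind has a start and an end, and staff need to be able to apply both to the same person. Here the end point is looser than the start on the diastolic side. Because the trigger is joined by and/or, diastolic pressure alone is enough to set it off. A subject can then be classed as having severe symptomatic hypertension while already being below the pressure to which the plan says it must be reduced.

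The stake is patient safety. Some subjects have had antihypertensive medication stopped in order to take part, and this rule is part of what protects them. If the end condition is satisfied on the first day, the instruction to follow closely until the goal is reached has no content for that subject.

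**Working it through.** No sample size, power or error rate is involved. The check compares two regions of blood pressure.

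**Inputs**

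- Trigger (Data and Safety Monitoring Plan): SBP >160 or DBP >100; an office reading, confirmed by ambulatory monitoring.
- Goal (same section): 160/110, ambulatory. I take reaching it to mean SBP ≤160 and DBP ≤110.
- Entry ceiling (Inclusion/Exclusion criteria; Protocol): ambulatory mean 160/100.

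**Step 1: difference between goal and trigger**

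- Systolic: 160 − 160 = 0 mmHg.
- Diastolic: 110 − 100 = 10 mmHg. The difference from the entry ceiling is the same.

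**Step 2: where trigger and goal hold together**

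Inside the goal region SBP is ≤160, so the systolic limb of the trigger cannot be met. The trigger can hold only through DBP >100, while the goal requires DBP ≤110. The overlap is therefore SBP ≤160 and 100 < DBP ≤110.

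**Step 3: illustrative cases (confirmed ambulatory values)**

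| BP | Trigger met? | Goal already met? |
|---|---|---|
| 150/105 | Yes (105 >100) | Yes (150 ≤160, 105 ≤110) |
| 170/105 | Yes (both limbs) | Diastolic part only (170 >160) |
| 150/115 | Yes (115 >100) | No (115 >110) |

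The third subject shows the other consequence. If pressure falls from 150/115 to 150/108, close follow-up may end with the diastolic value still 108 − 100 = 8 mmHg above the trigger. The most this can be is 10 mmHg.

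**Step 4: comparison with the neighbouring rule**

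The urinary calcium/creatinine rule in the same section starts at a ratio >1.0 and follows the patient until it is <1.0. No value satisfies both conditions. The overlap is particular to the diastolic figures.

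**Step 5: are the two measures comparable?**

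The trigger begins with an office reading but needs ambulatory confirmation, and the goal is ambulatory, so they can be compared. What is not stated is which ambulatory summary applies. The Procedures section defines daytime, nighttime and 24-hour values, and neither the trigger nor the goal names one.

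**The case against.** The strongest reply is that the goal carries little weight. It is called initial and is to be reached over several days, after which outside care takes over. An entry ceiling and a first treatment target also serve different purposes, so they need not coincide. Much of this stands, and it rules out several stronger readings that a reader might infer.

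- *No treatment or reduction is called for at 150/105.* Not supported. Starting therapy follows from the trigger and is not conditional on the 160/110 figure.
- *Whether such a subject stays or is withdrawn is undefined.* Not supported. The evaluating physician decides, on clinical risk and on whether there is a cause that can readily be resolved. Separately, the investigator or a nurse caring for the patient can stop the study for a subject who might be harmed. Neither decision refers to the goal. An effect on the blood pressure data that rests on this reading falls with it.
- *All monitoring ends at 160/110.* Not supported. Subjects who remain are seen every 2 weeks for six weeks and then monthly. Those withdrawn for medical reasons after at least 8 weeks have checks every 4 weeks to week 16.
- *Every subject triggered with a diastolic value from 101 to 110 is already at goal.* Too broad. Systolic pressure must also be at or below 160.
- *The problem belongs to the washout.* Only in part. Subjects on no blood pressure drugs may also enroll, and the rule covers all subjects.

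What the reply does not remove is the text itself. The study's close follow-up is tied expressly to this one figure, no later study goal is given, and no reason is offered for the change from 100 to 110. The 4-weekly checks do not extend to subjects withdrawn before week 8, who depend on outside care.

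**Conclusion.** The point holds as an internal inconsistency in a safety rule. The trigger and the end of close follow-up differ by 10 mmHg diastolic and 0 mmHg systolic. For symptomatic, sustained cases with SBP ≤160 and confirmed DBP above 100 and up to 110, both conditions are true at once and the follow-up rule cannot be applied as written.

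The scope is limited to that rule. No effect on power, error rate or the planned analyses is shown, and the document gives no basis for saying how many subjects would fall in the overlap.

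The conclusion assumes that reaching 160/110 means both components at or below those values, and that ambulatory confirmation uses the same limits as the office reading. It is also open to reading whether the goal covers everyone who is triggered or only those without a primary care doctor, who are mentioned immediately before it. The overlap is the same on either reading; only the group it applies to changes.

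The correction is worth making because this is a decision threshold in a safety rule and it is cheap to put right.

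**What to change.** The sponsor's clinicians should reconcile the diastolic figures for the trigger and the goal in the Data and Safety Monitoring Plan, checking them against the ambulatory ceiling in the Inclusion/Exclusion criteria and Protocol sections. The result should let staff apply both the trigger and the end of close follow-up to a subject with an isolated diastolic rise. Which figure stands is for the clinicians to decide; this review takes no position. The amended text should also name the ambulatory summary (24-hour, daytime or nighttime) used to confirm the trigger and to judge the goal, and say which subjects the goal covers.

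The cost is a short protocol amendment. Sample size and analysis are unaffected.
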